6.2 DETAILS OF TRIAL PROCEDURES AT SELECTED VISITS

6.2.1 Screening period

After having been informed about the trial, all subjects will give their written informed consent in accordance with GCP and local legislation prior to enrolment in the study.

For information regarding laboratory tests (including drug and virus screening), ECG, vital signs, and physical examination, refer to [Sections 5.2.3](#) to [5.2.5](#).

6.2.2 Treatment period

Each subject will receive one dose of the respective trial medication (BI 655088 or placebo) at Visit 2.

Trial medication will be administered as IV infusion by the investigating physician or his designee. Details on treatments and procedures of administration are described in [Section 4.1.4](#).

Study participants will be admitted to the trial site in the evening of Day -1 and kept under close medical surveillance for at least 48 h following the start of infusion. The subjects will then be allowed to leave the trial site after formal assessment and confirmation of their fitness by the investigator or designee. On all other study days, the study will be performed in an ambulatory fashion.

For details on time points and procedures for collection of blood samples for PK analysis, refer to [Flow Chart](#) and [Section 5.5.2](#).

The safety measurements performed during the treatment period are specified in [Section 5.2](#) of this protocol and in the [Flow Chart](#). For details on time points for all other trial procedures, refer to the [Flow Chart](#). AEs and concomitant therapy will be assessed continuously from screening until the end of trial examination.

6.2.3 End of trial period

For AE assessment, laboratory tests, recording of ECG and vital signs, and physical examination during the end of trial period, see [Sections 5.2.2](#) to [5.2.5](#).

Subjects who discontinue before the end of the treatment period should undergo the end of trial visit.

All abnormal values (including laboratory parameters) that are judged clinically relevant by the investigator will be monitored using the appropriate tests until a return to a medically acceptable level is achieved. Adverse events persisting after trial completion must be monitored until they have normalised or have been sufficiently characterised.

The end of the trial as a whole is defined by the 'last regular visit completed by last subject' or 'end date of the last open AE' or 'date of the last follow-up test' or 'date of an AE has been decided as sufficiently followed-up', whichever is latest.

7. STATISTICAL METHODS AND DETERMINATION OF SAMPLE SIZE

7.1 STATISTICAL DESIGN – MODEL

The trial design and dose groups are outlined in [Section 3.1](#) and discussed in [3.2](#).

7.1.1 Objectives

The primary objective of this trial is to investigate the safety and tolerability of BI 655088 in healthy male subjects following intravenous infusion of single rising doses of Within the parallel group design the treatment groups (dose levels and pooled placebo) will be compared by using descriptive statistics. The primary endpoint is defined in [Section 5.2.1](#). Inferential statistics is not planned (as explained in [Section 7.2](#)).

The secondary objective is the exploration of the pharmacokinetics (PK) and pharmacodynamics (PD) of BI 655088. Endpoints as specified in [Section 5.5.1](#) and [5.6.1](#) will be analysed by descriptive statistics. Secondary endpoints C_{max} , AUC_{0-tz} , and $AUC_{0-\infty}$ as defined in [Section 5.5.1.1](#) will be subjected to analysis of dose proportionality by use of the power model.

7.2 NULL AND ALTERNATIVE HYPOTHESES

Safety and tolerability of the different dose groups of BI 655088 are to be determined on the basis of the investigated parameters in comparison to placebo. It is not planned to test any statistical hypotheses with regard to these variables in a confirmatory sense. Instead, they will be described in their entirety and evaluated by descriptive statistical methods.

Confidence intervals will be computed and will have to be interpreted in the perspective of the exploratory character of the study, i.e. confidence intervals are considered as interval estimates for effects.

7.3 PLANNED ANALYSES

The following analysis data sets will be used in this trial:

The Randomised set includes all randomised subjects, whether treated or not. This set will be used for Listings. Subjects not randomised will not be analysed in the CTR.

The Treated set (TS) includes all subjects who were dispensed study medication and were documented to have taken at least one dose of investigational treatment. This set will be used for analyses of safety data, refer to [Section 7.3.3](#).

The PK parameter analysis set (PKS) is a per protocol set with regard to PK endpoints, refer to [Section 7.3.2](#). A full analysis set in the sense of ICH E9 will not be used in this trial.

Adherence to the protocol (such as inclusion/exclusion criteria, times of measurement, compliance with intake of trial medication, treatment dispensing errors, prohibited concomitant medication, completeness and consistency of data) will be checked. Important

protocol violations will be identified no later than in the Report Planning Meeting and provided in the TSAP.

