3. DESCRIPTION OF DESIGN AND TRIAL POPULATION

3.1 OVERALL TRIAL DESIGN AND PLAN

This single-rising dose trial is designed as single-blind, partially randomised, and placebo-controlled within parallel dose groups. “Partially” means that randomisation is done only in the second half of subjects of each dose level. For safety reasons the first half of subjects within each dose group will be administered study drug in a fixed sequence which is unknown to the volunteers: first subject active, second placebo, third active, fourth active.

A total of 48 healthy male subjects is planned to participate in the trial, according to 6 sequential groups comprising 8 subjects per group. However, additional subjects may be entered to allow testing of intermediate doses within the planned dose range on the basis of experience gained during trial conduct (e.g. preliminary PK data), i.e. the actual number of subjects entered may exceed 48. Such changes may be implemented via non-substantial CTP Amendments.

Within each dose group, 6 subjects will receive the active drug and 2 will receive placebo. Only one dose is tested within each dose group. Each dose group will consist of 3 cohorts which will be treated subsequently for safety reasons (see also [Section 2.3](#)).

The dose groups to be evaluated are outlined in [Table 3.1: 1](#) below.

Table 3.1: 1 Dose groups

Dose Group	1	2	3	4	5	6
Dose (mg)						
Number of subjects	8	8	8	8	8	8
Subjects receiving placebo	2	2	2	2	2	2
Subjects receiving active drug	6	6	6	6	6	6
Subject numbers						
Replacement numbers						

The dose groups will be investigated consecutively in ascending order of doses, maintaining a time interval of at least 21 days between the first drug administration in the previous dose group and treatment of a subject in the subsequent dose group. The decision to proceed to the next dose group will be based upon the safety and tolerability data of the preceding dose groups. The next dose will only be given if, in the opinion of the investigator, no safety concerns arose in the preceding dose group (i.e. no dose-limiting events occurred) and if none of the pre-specified trial-specific stopping criteria were met (refer to [Section 3.3.4.2](#)).

A documented Safety Review must take place prior to each dose escalation, but not earlier than 7 days after administration of last subject of a given dose level. Furthermore, an unscheduled safety review meeting can be requested anytime for any reasonable cause by the

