4.1.2 Method of assigning subjects to treatment groups

Prior to the screening visit, subjects will be contacted in writing and informed about the planned visit dates. The subjects willing to participate will be recruited to dose groups and cohorts according to their temporal availability. As soon as enough subjects have been allocated to a dose cohort, the following subjects will be allocated to one of the other dose cohorts. Therefore, the allocation of subjects to dose cohorts is not influenced by trial personnel, but only by the subjects' temporal availability. As the study includes healthy subjects from a homogenous population, relevant imbalances between the dose groups are not expected.

The randomisation list with study subject numbers and allocated treatments will be provided to the trial site in advance. The allocation of subjects to study subject numbers will be performed prior to the administration of trial medication in ascending order (e.g. in dose group 1 the first subject will be the next ...). Subjects will be allocated to a study subject number by the order of their subscription for the trial. Once a subject number has been assigned, it cannot be reassigned to any other subject.

The randomisation procedure is described in [Section 7.5](#).

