7.5 RANDOMISATION

Subjects will be randomised within each dose group in a 3:1 ratio, which reflects the ratio of subjects receiving active drug to placebo. Due to the fixed drug administration of the 4 first subjects within each dose group (1st subject active, 2nd subject placebo, 3rd and 4th subject active), the trial is called “partially-randomised”. Each dose group consists of 3 cohorts. The random numbers are assigned to the cohorts sequentially per dose group.

The sponsor will arrange for the randomisation as well as packaging and labelling of trial medication. The randomisation list will be generated using a validated system, which involves a pseudo-random number generator and a supplied seed number so that the resulting allocation is both reproducible and non-predictable.

The randomisation list will contain additional blocks to allow for subject replacement (refer to [Section 3.3.5](#)).

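### Does the Section 7.3 rule against analysing non-randomised subjects remove the fixed-sequence half of every dose group?

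*Protocol*

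**What the plan says.** Protocol Section 7.3 defines three sets. The Randomised set comes first: "The Randomised set includes all randomised subjects, whether treated or not. This set will be used for Listings". The next sentence is the one at issue: "Subjects not randomised will not be analysed in the CTR". The Treated set follows. It requires documented administration of study medication and sets no condition on how treatment was allocated; its use is stated as "This set will be used for analyses of safety data". Section 7.3.2 builds the PK parameter analysis set from the Treated set.

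On allocation, Section 3.1 says that "randomisation is done only in the second half of subjects of each dose level", and that the first half of each group is dosed in a fixed order: active, placebo, active, active. Section 7.5 is looser. It opens with "Subjects will be randomised within each dose group in a 3:1 ratio", then gives the reason for the partial label ("Due to the fixed drug administration of the 4 first subjects within each dose group") and adds: "The random numbers are assigned to the cohorts sequentially per dose group". Section 4.1.2 describes a single list: "The randomisation list with study subject numbers and allocated treatments will be provided to the trial site in advance".

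**The concern.** If randomised has the meaning that Section 3.1 gives it, the fixed-sequence subjects are not randomised, and Section 7.3 says such subjects are not analysed. That would remove half of the trial, including the first subjects exposed at every dose level. It would also contradict the Treated set definition in the same section.

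The stake under that reading would be real. The primary endpoint is the number of subjects with drug-related adverse events, and each dose level would hold 3 active subjects instead of 6. The protocol gives no event rate. For assumed true rates of 5%, 10% and 30%, the chance of seeing at least one event at a dose level would fall from 26% to 14%, from 47% to 27%, and from 88% to 66%. Listings based on the Randomised set might also cover 24 subjects while the tables cover 48.

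**Working it through.** **Reproducing the planned numbers.** Section 3.1 gives 6 groups of 8, each with 6 active and 2 placebo.

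- Total: 6 × 8 = 48, as in Section 7.6.
- Active: 6 × 6 = 36. Placebo: 6 × 2 = 12.

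**Splitting by method of allocation.** The fixed order (active, placebo, active, active) is 3 active and 1 placebo per group. The rest of each group is 6 − 3 = 3 active and 2 − 1 = 1 placebo.

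| | Active | Placebo | Total |
|---|---|---|---|
| Fixed sequence, 6 groups | 6 × 3 = 18 | 6 × 1 = 6 | 24 |
| Randomised, 6 groups | 6 × 3 = 18 | 6 × 1 = 6 | 24 |
| All | 36 | 12 | 48 |

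The literal reading would therefore leave out 24 of 48 subjects. The 3:1 ratio in Section 7.5 does not show which subjects the word covers, because it holds for all eight (6:2), for the fixed four (3:1) and for the last four (3:1).

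**The detection figures given above.** With n active subjects and true rate p, the chance of at least one event is 1 − (1 − p)^n. For p = 0.10: 1 − 0.9^6 = 0.469 and 1 − 0.9^3 = 0.271. For p = 0.05: 0.265 and 0.143. For p = 0.30: 0.882 and 0.657. They matter only if the safety analysis really ran on 3 active subjects per dose.

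**Which subjects each analysis uses.**

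- Safety and primary endpoint (7.3, 7.3.1, 7.3.3): the Treated set, entered by dosing alone. All 48 planned subjects qualify once dosed.
- Placebo comparison (7.3.3): everyone who received placebo, whatever the dose group, so 12 and not 6.
- Pharmacokinetics (7.3.2): Treated set members with at least one PK parameter not excluded. The listed grounds for exclusion are protocol violations and non-evaluability; method of allocation is not among them. Section 7.3.5 still reports individual values for those outside the set.
- Reporting of withdrawals (3.3.4.1): anyone who leaves after dosing is reported in the trial report, again without a condition on randomisation.

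**What the sentence in 7.3 most plausibly means.** Section 4.1.2 has one list pairing subject numbers with treatments. Numbers are taken in ascending order, and the example there starts with the first subject of dose group 1, who belongs to the fixed sequence. Section 7.5 assigns the random numbers to the cohorts, and Section 2.3 makes the fixed-sequence subjects the first two of the three cohorts. Section 3.3.5 gives a replacement the treatment of the subject he replaces, although Section 7.5 provides for replacements on the same list; so a place on the list does not imply allocation by chance. On this reading the sentence excludes people who never received a number, such as screening failures, and 0 of the 48 are affected.

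**The case for a change.** The strongest case for a change is that this is not a detail left to the statistical analysis plan. The protocol states an exclusion rule, and under the only explicit account of randomisation it gives, in Section 3.1, the rule is wrong for this design. No passage defines randomised as holding a list number. A later plan that followed the sentence literally would be wrong, and one that ignored it would depart from the protocol. There is a second mismatch: the Randomised set takes in subjects whether treated or not, while Section 3.3.4.1 keeps data from undosed subjects out of the database and the report. Rewording would cost a few sentences.

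Part of this stands. The word is used in two senses, and the listing population can be read as 24 or 48. The claim does not hold equally for both design sections, however: Section 7.5 describes fixed administration but never says that the first four are not randomised, and its opening sentence speaks of randomising within the whole group. The specific provisions for safety, placebo pooling and PK all point the same way, and an analyst cannot apply them and also drop the fixed-sequence subjects.

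Rewording also carries a risk. Stating in Section 7.5 that only the last four subjects are randomised, while leaving the Randomised set as it is, would fix that set at 24 subjects and create the listing mismatch that is now only one possible reading.

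**Conclusion.** The clash in wording is real, but it is a clerical inconsistency. Literally it covers 24 of 48 subjects; in every safety and PK analysis that the protocol specifies, it removes none. Only the population for listings is ambiguous, and no estimate comes from a listing. An analyst working from the Treated set, the PK set and the pooled placebo definition would include the fixed-sequence subjects without further instruction, so correcting the sentence would alter no result or conclusion.

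This rests on two assumptions. The first is that the specific set definitions prevail over the general sentence beside them, which is the only way the section can be applied. The second is that the fixed-sequence subjects hold numbers on the randomisation list, which Sections 4.1.2 and 7.5 indicate but do not state outright. If the second failed, the effect would still be confined to listings. No change to the plan is needed.

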7.3.1 Primary analyses

Analysis of safety and tolerability is described in [Section 7.3.3](#).

7.3.2 Secondary analyses

The secondary parameters (refer to [Section 5.5.1](#)) will be calculated according to the BI Standard Operating Procedure (SOP) ‘Standards and processes for analyses performed within Clinical Pharmacokinetics/Pharmacodynamics’ ([001-MCS-36-472](#)).

Plasma concentration data and parameters of a subject will be included in the statistical pharmacokinetic (PK) analyses if they are not flagged for exclusion due to a protocol violation relevant to the evaluation of PK (to be decided no later than in the Report Planning Meeting) or due to PK non-evaluability (as revealed during data analysis, based on the criteria specified below). Exclusion of a subject’s data will be documented in the CTR.

Relevant protocol violations may be:

- Incorrect trial medication taken, i.e. the subject received at least one dose of trial medication the subject was not assigned to
- Incorrect dose of trial medication taken
- Use of restricted medications.

Plasma concentrations and parameters of a subject will be considered as non-evaluable, if for example:

- Missing samples/concentration data at important phases of PK disposition curve

The PK parameter analysis set (PKS) includes all subjects in the Treated Set (TS as defined in [Section 7.3](#)) who provide at least one PK parameter that was not excluded according to the description above.

Assessment of dose proportionality

Dose proportionality will be assessed using the pharmacokinetic endpoints C_{max} , AUC_{0-tz} , and $AUC_{0-\infty}$ as specified in [Section 5.5.1.1](#).

The basic model for the investigation of dose proportionality will be a power model that describes the functional relationship between the dose and PK endpoints.

$$\exp(Y_{ij}) = \alpha' * \exp(X_i)^\beta * \epsilon'_{ij}$$

The model consists of a regression model applied to log-transformed data. The corresponding ANCOVA model includes the logarithm of the dose as a covariate.

Together with $\alpha' = \exp(\alpha)$ and $\epsilon'_{ij} = \exp(\epsilon_{ij})$, taking natural logarithms converts this model to a linear form as follows:

$$Y_{ij} = \alpha + \beta * X_i + \varepsilon_{ij}$$

where

Y_{ij}	logarithm of the pharmacokinetic endpoint for subject j at dose level i; where $i = 1, 2, \dots, j = 1, 2, \dots, n_i$;
α	intercept parameter;
β	slope parameter;
X_i	logarithm of dose i;
ε_{ij}	random error associated with subject j at dose level i (assumed to be independent and identically normally distributed).

This equation can be fit as a linear regression model.

Based on the estimate for slope parameter (β), a 2-sided 95% CI for the slope will be computed. Perfect dose proportionality would correspond to a slope of 1. The assumption of a linear relationship between the log-transformed pharmacokinetic endpoint and the log-transformed dose will be checked.

If dose proportionality over the entire dose range investigated cannot be shown, an attempt will be made to identify dose range(s), where dose proportionality can be assumed.

Graphical displays

To support the analyses of dose proportionality, graphical representations of the data might be created. These might include (but are not limited to) individual time-courses of plasma concentrations and the (geometric) mean plasma concentration time profiles as well as C_{max} , AUC_{0-tz} , and $AUC_{0-\infty}$ versus dose.

7.3.3 Safety analyses

Safety will be assessed for the endpoints listed in [Section 5.2.1](#). The TS as defined in [Section 7.3](#) will be included in the safety analyses.

Safety analyses will be descriptive in nature and will be based on BI standards.

Treatments will be compared in a descriptive way. The placebo control group in the safety evaluation will consist of all placebo treated subjects, regardless of the dose group in which they were treated. The active treatment groups will be compared to the placebo group in a descriptive way. Tabulations of frequencies/proportions will be used for the evaluation of categorical (qualitative) data, and tabulations of descriptive statistics will be used to analyse continuous (quantitative) data.

The analyses will be done by 'treatment at onset'.

Measurements (such as ECG, vital signs, or laboratory parameters) or AEs will be assigned to treatments (see [Section 4.1](#)) based on the actual treatment at the planned time of the measurement or on the recorded time of AE onset (concept of treatment emergent AEs). Therefore, measurements planned or AEs recorded prior to administration of trial medication will be assigned to 'screening', those between start of drug administration until the end of trial visit will be assigned to the treatment period, and those after the end of trial examination will

be assigned to ‘post-treatment’. These assignments including the corresponding time intervals will be defined in detail in the TSAP.

Adverse events will be coded using the Medical Dictionary for Regulatory Activities (MedDRA). Frequency, intensity and causal relationship of AEs will be tabulated by treatment, primary system organ class and preferred term. SAEs, AESIs (see [Section 5.2.2.1](#)) and other significant AEs (according to ICH E3) will be listed separately.

Laboratory data will be compared to their reference ranges. Values outside the reference range will be flagged. Additionally, differences from baseline will be evaluated. Results of the oGTT, i.e. further plasma glucose and serum insulin measurements will be evaluated in the same way as laboratory data but presented separately. In addition, graphical representations of individual time-courses of plasma glucose and insulin measurements and the (geometric) mean time profiles will be presented.

Area under the curve will be calculated for glucose and insulin according to the linear trapezoidal rule.

Changes in AUCs for glucose and insulin (oGTT measurements) from baseline to post-treatment will be compared between BI 655088 and placebo.

Descriptive statistics of bleeding time at the time points given in the [Flow Chart](#) and for the difference from baseline will be provided.

Descriptive statistics of vital signs and for the difference from baseline will be presented per planned time. ECG data will not be listed but clinically relevant abnormal findings will be reported as adverse events.

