5.2.3.1 Oral glucose tolerance test (oGTT)

An oGTT will be performed on the morning of Day -5 to -1 (baseline) and Day 29. After blood drawing for determination of fasting plasma glucose and serum insulin, 75 g of glucose will be dissolved in 200 mL water and swallowed by the subject. Thirty minutes, 1, 2 and 3 hours after intake of the glucose solution, further blood samples will be taken for glucose and insulin measurement. Blood samples for glucose measurements will be drawn in a 2 mL sodium fluoride (NaF) tube. Blood samples for insulin measurements will be drawn in a 2.5 mL serum tube.

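### Does comparing the change in oGTT glucose and insulin AUC with placebo, with no baseline covariate named, weaken the comparison?

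*Protocol*

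**What the plan says.** The oGTT is done twice per subject (Protocol Section 5.2.3.1): "An oGTT will be performed on the morning of Day -5 to -1 (baseline) and Day 29". Section 7.3.3 derives the summary measure: "Area under the curve will be calculated for glucose and insulin according to the linear trapezoidal rule". It then states the comparison: "Changes in AUCs for glucose and insulin (oGTT measurements) from baseline to post-treatment will be compared between BI 655088 and placebo". No model and no covariate is named, and adjustment is not excluded either.

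The setting is descriptive throughout. Section 7.3.3 says that "tabulations of descriptive statistics will be used to analyse continuous (quantitative) data" and "The active treatment groups will be compared to the placebo group in a descriptive way". Section 7.1.1 names the units compared: "Within the parallel group design the treatment groups (dose levels and pooled placebo) will be compared by using descriptive statistics"; it also says that inference is not planned. Section 7.2 rules out confirmatory testing and reads any interval as exploratory: "confidence intervals are considered as interval estimates for effects".

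The group sizes come from Section 3.1: "Within each dose group, 6 subjects will receive the active drug and 2 will receive placebo". Section 7.3.3 pools the placebo subjects of all dose groups.

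**The concern.** Each dose-level comparison rests on one change per analyte in 6 subjects, set against 12 on placebo. In groups this small the baseline means will often differ by chance. A difference in mean change over-corrects for such a difference unless baseline and follow-up are perfectly correlated. A dose group that happens to start high then tends to show a fall that has nothing to do with the drug. The baseline AUC is already collected, so a linear model with baseline as covariate would remove this dependence and, at low to moderate correlation, give a tighter estimate. At stake would be a false hint of a glucose or insulin effect at a dose level, or a real one masked.

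**Working it through.** **Inputs from the protocol.** Six dose groups of 8, each with 6 active and 2 placebo (Section 3.1).

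- Total: 6 × 8 = 48, which matches the planned sample size in Section 7.6.
- Pooled placebo: 6 × 2 = 12.
- All active: 6 × 6 = 36.
- One dose level against placebo: 6 versus 12.

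**Inputs not in the protocol.** The between-subject SD of the AUC and the correlation ρ between baseline and Day 29. Results are therefore in units of one between-subject SD. Assumptions: ρ of 0.3, 0.5, 0.7 and 0.9, equal SD at both times, complete data.

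**Step 1: size of a chance baseline difference.** Its SD is √(1/6 + 1/12) = 0.50, so a difference beyond 0.5 SD in either direction occurs in about 32% of such comparisons. If the sentence means all active against placebo, the SD is √(1/36 + 1/12) = 0.33 and the frequency 13%.

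**Step 2: what plain change does with a chance difference d.** The estimate shifts by −(1 − ρ)d.

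**Step 3: precision of each method.** One model holds six dose levels and pooled placebo.

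- Change: SE = 0.50 × √(2(1 − ρ)), 48 − 7 = 41 df.
- Adjusted: SE = 0.50 × √(1 − ρ²) × √(1 + 1/39), 40 df. The last factor is the average cost of estimating the slope.

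At ρ = 0.5 these are 0.50 × 1.000 = 0.500 and 0.50 × 0.866 × 1.013 = 0.439.

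**Step 4: what adjustment does with a stable difference.** Suppose a dose group comes from a population whose AUC is higher by d at both times, with no drug effect. The expected difference in change is d − d = 0. The expected adjusted difference is d − ρd = (1 − ρ)d.

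| ρ | SE, change | SE, adjusted | 95% interval shorter by | Shift in plain change, chance d = 0.5 | Bias of adjusted estimate, stable d = 0.5 |
|---|---|---|---|---|---|
| 0.3 | 0.592 | 0.483 | 18% | −0.35 | +0.35 |
| 0.5 | 0.500 | 0.439 | 12% | −0.25 | +0.25 |
| 0.7 | 0.387 | 0.362 | 7% | −0.15 | +0.15 |
| 0.9 | 0.224 | 0.221 | 1% | −0.05 | +0.05 |

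The variances are equal where (1 + ρ)/2 × (1 + 1/39) = 1, that is at ρ = 0.95. Simulation confirmed the standard errors (20,000 trials per ρ). For step 4, a simulation of 8,000 trials per ρ gave mean adjusted estimates of 0.34, 0.24, 0.15 and 0.05, with plain change within 0.015 of zero.

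**Step 5: which mechanism applies here.** The protocol does not settle it.

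- Section 4.1.2 fills dose groups by when subjects are available, not by randomisation, and expects no relevant imbalance.
- Sections 3.1 and 7.5 fix the treatment of the first four subjects of each group.
- For any dose level, 12 − 2 = 10 of the 12 placebo subjects come from other dose groups.
- Section 11 records that the smoking exclusions were revised and that the trial was on temporary hold, so recruitment conditions were not constant.

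A baseline difference between a dose level and pooled placebo may thus be chance, stable, or both.

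**The case for a change.** The strongest case for adjustment is that Section 7.3.3 goes beyond tabulation: it names the derived variable and the contrast, and so could reasonably name the covariate too. The data exist, the cost is one degree of freedom, and Section 7.2 leaves room for exploratory intervals. If baseline differences are pure chance, adjustment removes the dependence on them and is the more precise method on average for any ρ below about 0.95. Non-random filling of dose groups can itself be read as a reason to adjust, since the groups may differ at baseline.

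The arithmetic stands, and an adjusted estimate beside the planned summaries would be compatible with the protocol. The rest does not carry the point:

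- Whether to use a covariate in an exploratory safety summary is commonly settled in the statistical analysis plan. Silence here contradicts nothing and closes off nothing.
- The gain in precision is a shorter interval, yet the protocol specifies none for this comparison. Six dose levels and two analytes would add 6 × 2 = 12 modelled intervals to a section that plans tabulations.
- Non-random filling works in both directions. Against stable group differences it is plain change that is unbiased, and the adjusted estimate is off by the same amount that is charged to plain change in the chance case.

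**Conclusion.** The concern does not hold. The planned change in AUC is a legitimate descriptive measure, stated consistently with Sections 7.1.1, 7.2 and 7.3.3. No escalation or stopping rule in the protocol is tied to this comparison, and baseline AUC remains available should an adjusted analysis be wanted.

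Adjustment would be a choice between two methods, each right under a different assumption. Under pure chance imbalance it shortens a 95% interval by 18% to 1% for ρ from 0.3 to 0.9. Under a stable difference of 0.5 SD it introduces a bias of 0.35 to 0.05 SD over the same range. These figures rest on an assumed ρ, equal SDs and complete data. The judgement that nothing is wrong does not depend on them: it rests on the descriptive purpose, on the absence of any model fixed in the protocol, and on allocation to dose levels that is not fully randomised.
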